a. Study design, including the sequence and timing of study procedures (distinguish research procedures from those that are part of routine care).

This is a within subject pilot study that plans to enroll 20 chronic (more than 6 months) SCI patients as per recruitment matrix in Table 1. This pilot study will provide preliminary evidence with respect to both Hypothesis 1 and Hypothesis 2 (see above). Organization of a larger trial is planned, the detail design of which will depend upon the outcomes from this study, and subjects will be recruited from individuals already undergoing rehabilitative interventions at the International Center for Spinal Cord Injury (ICSCI) at the Kennedy Krieger Institute and nearby military medical centers (Walter Reed, Baltimore VA). In addition to their already prescribed rehabilitation regimen, the eligible subjects will engage in a virtual reality sailing program (VSail) once a week, 1h/session for 12 weeks. The subjects will be assessed using a battery of physical and neurological indicators before starting the training (baseline), after 6 weeks and 12 weeks of training, and at 6 and 12 months following the completion of the training. During each training visit outcomes will be assessed by the trainer. The study timeline is found in Figure 1.

	High Tetra (C1-C5)	Low Tetra (C6-C8)	High Para (T1-T6)	Low Para (T7-T12)	Coda Equina (L1-S1)
Motor Complete (A-B)	2	2	2	2	2
Motor Incomplete (C-D)	2	2	2	2	2

Table 1: Recruitment Matrix

[figure not shown]

Figure 1: Study Time Line

All activities will be conducted at Kennedy Krieger Institute and are supervised by the Principal Investigator.

(1) Study Intervention:

All activities will be conducted at Kennedy Krieger Institute by a VSail trainer.

While undergoing the virtual sailing training, the subjects will use a VSail-Access simulator (Virtual Sailing, Melbourne, Australia). The VSail simulator will be set in the Access Dinghy mode. The VSail sailing parameters will be set to the subjects skill set and progression in the training program: wind speed from minimum (8 knots) to moderate strength (14 knots), pneumatic rams (simulating the heeling of the hull) on or off.

The subjects will be transferred to the VSail cockpit and secured. Following the trainer's instruction, the subject will sail the simulator around virtual courses displayed on a computer screen, using a joystick to control the rudder angle and a mainsheet to control the set of the sail.

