Training will be interrupted for fatigue (17 or over on the Rate of Perceived Exertion (RPE) scale), signs and symptoms of Autonomic Dysreflexia (headache, sweating, facial flushing, goose bumps/piloerection, irritability, crying, sudden and profuse sweating above injury level, intense head/neck tingling), symptomatic orthostatic hypotension (dizziness, light headedness, palpitations, sudden vision loss, profuse sweating). Session will resume when symptoms resolve.

All subjects will continue their already prescribed rehabilitation regimen as per clinical plan and indications.

(2) Study Assessments:

Version: 2
Date: January 13th 2015
Principal Investigator: [name].
Application Number: NA_00044093

This pilot study will include a combination of pre- and post-qualitative assessments, as well as 6 and 12 month follow-up. All study assessments will be conducted at Kennedy Krieger Institute by a study team member trained in the assessment. The data collection schedule is in Table 2.

(a)Vital Signs: This is a routine test performed for people with spinal cord injury. Resting heart rate and blood pressure in sitting position. This test will be performed on all subjects.

(b)Pulmonary Function Test (PFTs): This is a routine test performed for people with spinal cord injury. Three respiratory functions will be measured: Vital Capacity (VC) is the maximal amount of air that can be exhaled after a maximal inhalation; Negative Inspiratory Force (NIF) is the ability to take a deep breath in and to generate a cough strong enough to clear secretions; Peak Cough Flow (PCF) measures the expiratory muscle force and the ability to cough. This test will be performed on all subjects.

(c)ASIA Test: This is a routine test performed for people with spinal cord injury. The ASIA (American Spinal Injury Association) exam assesses motor function at 10 key muscles in the body and light touch and pinprick sensation at 28 key points on each side of the body. It is also used to classify injury level and severity. This test will be performed on all subjects.

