(i) Sailing Ability Questionnaire: This is a routine test performed for people involved in a training program. This questionnaire will assess the subject's views about sailing, as well as the subject's perceived sailing abilities. This questionnaire will be used for all subjects.

(j) Cardio-Vascular Monitoring: This is a routine test performed for people undergoing a cardio-vascular type exercise. This test will be performed on all subjects. The following vital sign will be recorded:

- Fatigue as per RPE.
- Blood pressure and heart rate with any sign or symptom of autonomic dysreflexia (AD) (manifested as pilo-erection, sudden and profuse sweating above injury level, facial flushing, intense head/neck tingling, headache) or signs of orthostatic hypotension (dizziness, light headedness, palpitations, sudden vision loss, profuse sweating).

(k) Sailing Score: This is a routine function of the VSail-Access simulator. The score will be based on the ability to perform specific sailing maneuvers (steering predetermined courses, sail trimming, tacking, gybing, mark rounding), and the ability to navigate a simple course around marker buoys (triangular configuration) on the computer screen within a predetermined time. This test will be performed on all subjects.

(l) Weekly Diary: This is a routine test performed for people in a clinical study. A weekly diary will be kept by the subject. The following events will be recorded: change in medical status, change in medication, change in prescribed rehab program. The study coordinator will review the diary with the subject every week. This will be done for all subjects.

(m) Follow-up Questionnaire: This is a routine test performed for people involved in a training program. This questionnaire will assess the subject's views about sailing on the water after been in the VSail training program, as well as the subject's perceived sailing abilities.. This questionnaire will be used for all subjects.

b. Study duration and number of study visits required of research participants.

The study will last one (1) year, with an active training phase of 12 weeks. The subjects will continue their already prescribed treatment rehabilitation regimen, and attend one hour session of virtual reality sailing once a week for 12 weeks. They will return at 6 and 12 months to be assessed. The study timeline is found in Figure 1 and the data collection schedule in Table 2.

	Initial	Training	Weekly	6 Weeks	12 Weeks	6 Months	12 Months

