	2 hours	1 hours	10 minutes	2 hours	2 hours	10 minutes	10 minutes
Vital Signs	√			√	√		
PFTs	√			√	√		
ASIA	√			√	√		
SCI QL-23	√			√	√		
VR-36	√			√	√		
Functional Reach	√			√	√		
Trunk	√			√	√		
Grasp/Pinch	√			√	√		
Sailing Ability	√				√		
Cardio-Vascular		√					
Sailing Score		√					

Version: 2
 Date: January 13th 2015
 Principal Investigator: [name].
Application Number: NA_00044093

Diary				√				
Follow-up Q							√	√

Table 2: Data Collection Schedule

The following assessments will be performed at the Initial, and 12 Week visits:

- (a) Vital Signs (about 5 mins)
- (b) Pulmonary Function Test (about 5 mins)
- (c) ASIA (60 mins)
- (d) SCI QL-23 (about 10 mins)
- (e) VR-36 (about 10 mins)
- (f) Functional Reach Test (about 5 mins)
- (g) Level of Trunk Activation (about 5 mins)
- (h) Grasp/Pinch test (about 5 mins)
- (i) Sailing Ability Questionnaire (about 5 mins)

The following assessments will be performed at the 6 Week visits:

- (a) Vital Signs (about 5 mins)
- (b) Pulmonary Function Test (about 5 mins)
- (c) ASIA (60 mins)
- (d) SCI QL-23 (about 10 mins)
- (e) VR-36 (about 10 mins)
- (f) Functional Reach Test (about 5 mins)
- (g) Level of Trunk Activation (about 5 mins)
- (h) Grasp/Pinch test (about 5 mins)

The following assessments will be performed at all VSail training Visits:

- (j) Cardio-Vascular Monitoring (about additional 5 minutes to VSail session)
- (k) Sailing Score (about 5 minutes included in VSail session)

The following assessments will be performed weekly during the training:

- (l) Weekly Diary review (about 10 minutes), once a week only

The following assessments will be performed at the 6 Month and 12 Month visits:

- (m) Follow-up Questionnaire (about 10 mins)

c. Blinding, including justification for blinding or not blinding the trial, if applicable.

Not Applicable.

d. Justification of why participants will not receive routine care or will have current therapy stopped.

All subjects will continue to consistently perform their usual (“baseline”) amount of physical activity throughout the study, including clinic and home exercise program. “Baseline” activity is defined as amount of physical activity performed for at least 1 month prior to enrollment. Routine care will not be interrupted.

e. Justification for inclusion of a placebo or non-treatment group.

Not Applicable.

Version: 2
Date: January 13th 2015
Principal Investigator: [name].
Application Number: NA_00044093

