f. Definition of treatment failure or participant removal criteria.

Subjects may withdraw from the study at any time for any reason.

The subject may be removed from the study for any of the following reasons:

- a. The subject experiences a medical emergency that necessitates discontinuation of therapy
- b. The subject experiences a serious adverse event that is judged to be likely related to the therapy or is of severity that warrants discontinuation of treatment.
- c. For any medical reason at the discretion of the investigator.
- d. Subject is no compliant: participants who miss more than 3 sessions of training for the duration of the study.

g. Description of what happens to participants receiving therapy when study ends or if a participant's participation in the study ends prematurely.

Upon completion of the study, participants will be referred back to their treating SCI specialist who will be made aware of the treatment and follow-up. The same protocol will be followed for patients who terminate the study early. In the event of discontinuation due to adverse event, participants will be followed by the PI until resolution or stabilization of their adverse condition and then referred back to their treating SCI specialist.

Version: 2
Date: January 13th 2015
Principal Investigator: [name].
Application Number: NA_00044093

Inclusion/Exclusion Criteria

h. Inclusion:

- a. Males and Females, age 18-75, all ethnic groups.
- b. Spinal Cord Injury.
- c. Chronic injury, > 6 months from the injury.
- d. All ASIA neurological levels (C1-S1) as per Table 1.
- e. All ASIA impairment scale A-D as per Table 1.
- f. Subjects are able to comply with procedures and follow-up.
- g. Subjects are medically stable, with no recent (1 month or less) inpatient admission for acute medical or surgical issues.

i. Exclusion:

- a. Cardiovascular disease as defined by previous myocardial infarction, unstable angina, requirement for anti platelet agents, congestive heart failure, or stroke NYHA Class III or IV, history of arrhythmia with hemodynamic instability.
- b. Uncontrolled hypertension (resting systolic BP > 160mmHg, or diastolic BP > 100mmHg consistently).
- c. Severe hypotension (systolic BP < 80 mmHg, or diastolic BP < 55 mmHg).
- d. Ventilator dependant subjects.
- e. Significant cognitive impairment.
- f. History of epileptic seizures.
- g. Unstable long bone fractures of the extremities.
- h. Subjects having Stage III or greater skin ulcerations.

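### After signs of autonomic dysreflexia, a session may restart on symptom resolution alone: the blood pressure already required at the event is not used, and no repeat is asked for

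*Protocol*

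**What the plan says.** Section 3.a(1), Study Intervention, stops training for three reasons: fatigue (17 or over on the exertion scale), signs of autonomic dysreflexia, and symptomatic orthostatic hypotension. One sentence then governs the restart after any of them: "Session will resume when symptoms resolve".

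Section 3.a(2)(j), Cardio-Vascular Monitoring, lists what is recorded during sessions. Besides the exertion rating, it asks for "Blood pressure and heart rate with any sign or symptom of autonomic dysreflexia (AD" (the list of signs that follows is left out here), and for the same two measurements with signs of orthostatic hypotension. It gives no limit, asks for no second reading and does not mention the restart.

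A reference value is planned. Section 3.a(2)(a) defines vital signs as "Resting heart rate and blood pressure in sitting position", and Table 2 schedules them at the Initial, 6 Week and 12 Week visits.

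On who is present, section 3.a(1) says "All activities will be conducted at Kennedy Krieger Institute by a VSail trainer". Section 6.b puts all sessions under the Principal Investigator's supervision. Section 6.b(1) adds that a trained study team member monitors subjects for these events (it cites the monitoring item as (i), where (j) is meant).

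**The concern.** Section 6.b(1) names the monitoring as the measure that keeps the risk of dysreflexia and hypotension low. By asking for blood pressure at the event, the protocol treats pressure as relevant to it. Yet the restart rule ignores the value: whatever the reading shows, the session goes on once the subject's symptoms are gone. If pressure were still raised at that moment, the written rule would be met all the same.

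What is at stake is the safety of subjects within a session. No endpoint, estimate or conclusion of the pilot is involved.

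**Working it through.** No figure in the protocol bears on this point, so the check sets the rules side by side.

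**Step 1. What stops a session, what is measured, and what releases it**

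| Event | Stops on | Measured at the event, 3.a(2)(j) | Release, 3.a(1) | Reading used for release? |
|---|---|---|---|---|
| Fatigue | Exertion rating of 17 or over | Exertion rating | Symptoms gone | No pressure reading required |
| Dysreflexia | Listed signs | Blood pressure, heart rate | Symptoms gone | No |
| Symptomatic orthostatic hypotension | Listed symptoms | Blood pressure, heart rate | Symptoms gone | No |

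Two of the three events call for a pressure reading. Neither reading enters the restart decision.

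**Step 2. Is there a second restart condition elsewhere in the available text?**

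- Section 6.b and 6.b(1): supervision and trained monitoring, with no restart criterion.
- Section 3.f, item c ("For any medical reason at the discretion of the investigator"): this governs removal from the study, not resumption within a session.
- Exclusion criteria b and c: resting pressure consistently above 160 systolic or 100 diastolic, and "Severe hypotension (systolic BP < 80 mmHg, or diastolic BP < 55 mmHg"). These are the only numerical pressure limits, and they apply at entry.
- Table 2: resting values at three visits, the first before training starts, so a baseline should be on file for every session. The restart rule does not refer to it.

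None of these supplies a condition beyond symptom resolution.

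**Step 3. Does the gap weigh equally on all three events?**

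No. Hypotension counts as a trigger only when it is symptomatic, so release on symptoms mirrors the trigger; what remains is that a required reading goes unused. Dysreflexia is a condition recognised through its signs, and the disappearance of signs is not the same statement as the end of the condition. Fatigue has no pressure component. Dysreflexia therefore carries the point.

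**Step 4. What kind of limit would close the gap?**

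A fixed ceiling alone is too weak. Take assumed values: resting systolic 95 mmHg, repeat reading 155 mmHg. Then 155 < 160, so the subject passes the ceiling, but 155 − 95 = 60 mmHg above the subject's own baseline. A comparison with baseline alone leaves no number at all in the rule. The two together cover both weaknesses. At the lower end, an eligible subject is not below 80 systolic or 55 diastolic at entry, so that floor does not bar anyone at their entry resting value.

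**The case against.** The strongest reply is that an episode is not handled by a trainer alone with one sentence to follow. A trained team member is monitoring, the Principal Investigator supervises, and a pressure reading has just been taken. These people can be expected to look at it before going on, and a repeat reading is the sort of detail that site clinical procedure may supply. The protocol also calls the risk minimal, and nowhere says that pressure stays abnormal once symptoms have cleared.

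Much of this stands, and it limits the point. It does not remove it: the protocol chose to state a restart rule, stated it as a single condition, and left out the measurement that it requires for the same event. Supervision reduces the risk but sets no restart condition.

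Three stronger readings are tempting, and the documents do not support them:

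- A reader might infer that all 20 × 12 = 240 planned sessions are exposed. The rule acts only in interrupted sessions, and no episode rate is given.
- A reader might infer that hypotension is left as open as dysreflexia. Step 3 of the working shows why it is not.
- A reader might infer that subjects will in fact restart at a raised pressure. The text shows only that the rule would allow it.

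**Conclusion.** The point holds for dysreflexia as a gap in a stated safety rule: symptom resolution is the sole written condition, so a restart at a still-raised pressure would comply with the protocol. Its size cannot be derived and may be zero. It rests on two assumptions that the protocol does not spell out: that pressure is a relevant measure of a dysreflexia episode, which the protocol implies by requiring the reading, and that pressure can lag behind symptoms, for which the protocol gives no evidence either way. This is a minor safety improvement, worth making because it is cheap.

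**What to change.** Keep the present sentence for fatigue. For dysreflexia, and as a simple extension for symptomatic orthostatic hypotension, write in section 3.a(1):

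> The session may resume only when symptoms have resolved and a repeat blood pressure and heart rate, taken by the trained monitor, are acceptable to the investigator relative to the subject's most recent resting values under 3.a(2)(a), with blood pressure not above 160/100 mmHg and not below 80/55 mmHg. Otherwise the session ends for that day and is not counted as missed under 3.f(d).

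The limits are the protocol's own entry limits, borrowed as a reference. The upper one excludes at entry only when exceeded consistently, so applying it to a single reading is somewhat stricter.

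**Cost.** One amended sentence and one repeat of a measurement already required, in a session that already allows for "Cardio-Vascular Monitoring (about additional 5 minutes to VSail session"). Some sessions may be cut short, with possible loss of that week's sailing score: 1 of 12, or 8.3% of a subject's scores. The last clause is needed because section 3.f(d) allows removal of "participants who miss more than 3 sessions of training for the duration of the study", that is, at least 4 of 12. Without it, sessions ended for safety could count toward removal.

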(d)Spinal Cord Injury Quality of Life Questionnaire (SCI QL-23): This is a routine test performed for people with spinal cord injury. The SCI QL-23 is a 23-item health-related quality of life questionnaire (weighted scale, aggregate score: GQOL: overall rating of life situation; FUNC: physical and social limitations; DEPR: distress and depressive feelings; PROB: perceived loss of independence and other issues relating to injury [Copyright © 1990 Health Care Research Unit, Sahlgrenska University Hospital, Sweden]). The subject will read the questionnaire and answer the questions; if needed ,assistance will be provided to record the answers on the form. The SCI QL-23 questionnaire will be used for all subjects.

(e)Veterans RAND 36-Item Health Survey (VR-36): This is a routine test performed for people with health related issues. The VR-36 is a health-related quality of life questionnaire (weighted scale, aggregate score [Copyright © Boston University School of Public Health, MA]. The subject will read the questionnaire and answer the questions; if needed, assistance will be provided to record the answers on the form. The VR-36 questionnaire will be used for all subjects.

(f)Functional Reach (FR) Test: This is a routine test performed for people with spinal cord injury. This test is used to evaluate trunk balance. This test is performed by patient reaching forward as far as they can while seated in their wheelchair. The distance traveled by the top of the reference shoulder is measured; 2 practice trials and 1 actual reach test is performed for the purpose of the study. The forward and lateral reach will be assessed on all subjects.

(g)Level of Trunk Activation: This is a routine test performed for people with spinal cord injury. This test will assess the activation of trunk muscle by asking the patient to perform a sit-up from the supine position. Using landmarks such as sterna angle, nipple line, supra-sternal notch, and ribs the lowest level of trunk activation will be determined. This test will be performed on all subjects.

(h)Grasp/Pinch Testing: This is a routine test performed for people with spinal cord injury. This is a standard test used to assess strength of grasp and lateral pinch. The Jamar dynamometer will be used to assess grasp and lateral pinch. This test will be performed on all subjects.

Version: 2
 Date: January 13th 2015
 Principal Investigator: [name].
Application Number: NA_00044093

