- i. Active sailor.
- j. Active drug or alcohol use or dependence that, in the opinion of the site investigator, would interfere with adherence to study requirements.

4. Drugs/ Substances/ Devices

a. The rationale for choosing the drug and dose or for choosing the device to be used.

The VSail-Access simulator (Virtual Sailing, Melbourne, Australia) is the first sailing simulator available for people with disabilities.

The VSail simulator is a generic sailboat cockpit powered by a pneumatic ram and custom designed software. The sailor sails the simulator around virtual courses displayed on a computer screen or overhead display in the same way as a real sailboat on water (a tiller to control the rudder angle, a mainsheet to control the set of the sail and body position to control heeling of the hull). Electronic sensors provide real time feedback to match the movements of the virtual sailboat displayed on the screen with those of the simulator. Sailors can select wind strength and conditions to suit their ability. The VSail-Access simulator is a variation on the VSail where the cockpit is fitted with a seat based on the design used for Access dinghies (<http://accessdinghy.org>).

b. Justification and safety information if FDA approved drugs will be administered for non-FDA approved indications or if doses or routes of administration or participant populations are changed.

Not applicable.

Version: 2
Date: January 13th 2015
Principal Investigator: [name].
Application Number: NA_00044093

c. Justification and safety information if non-FDA approved drugs without an IND will be administered.

Not applicable.

5. Study Statistics

a. Primary outcome variable.

(1) Ability to sail:

- (a) standard maneuvers: ability to perform specific sailing maneuvers (steering predetermined courses, sail trimming, tacking, gybing, mark rounding).
- (b) Ability to navigate a simple course around marker buoys (triangular configuration) on the computer screen within preset time.

(2) Quantitative health, welfare, self esteem and quality of life survey.

b. Secondary outcome variables.

- (1) ASIA (American Spinal Injury Association) scoring.
- (2) Cardio vascular health (pulmonary function test, vital signs).
- (3) Trunk control (functional testing of reach, level of trunk muscle activation).
- (4) Grip and pinch strength.

c. Statistical plan including sample size justification and interim data analysis.

This is a pilot study. No statistical analysis is planned.

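### Functional reach rests on a single recorded reach per visit, so full trial-to-trial error enters each subject's change; averaging three would remove part of it cheaply.

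*Protocol*

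**What the plan says.** Protocol section 3.a(2)(f) describes the test: "This test is performed by patient reaching forward as far as they can while seated in their wheelchair". On the number of trials it states that "2 practice trials and 1 actual reach test is performed for the purpose of the study", and on direction that "The forward and lateral reach will be assessed on all subjects". Nothing says that the practice reaches are written down or averaged, and nothing requires the same wheelchair, cushion or posture at each visit.

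Section 5.b lists trunk control as a secondary outcome, measured by reach and by level of trunk muscle activation. Section 3.a describes the design: "This is a within subject pilot study that plans to enroll 20 chronic (more than 6 months) SCI patients". Table 2 schedules reach at Initial, 6 weeks and 12 weeks, within two-hour visits, and the visit lists in section 3.b allow it about 5 minutes. There is no control group (section 3.e). Section 5.c says that no statistical analysis is planned, so no SD, reliability figure or change score is given for reach.

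**The concern.** With no comparison group, change within a subject is the only evidence that the study can give on trunk control. A change score carries measurement error from both visits. With one recorded reach at each, none of that error is averaged out.

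The number of recorded trials is a data-collection rule, so it has to be right in the protocol: if only one reach is written down, no later analysis can recover the others. Section 3.a also says that the detailed design of the planned larger trial will depend on this study's outcomes. An avoidably noisy reach measure would widen the pilot estimate and could inflate the SD carried into that planning.

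The seat raises a smaller, related matter. If a subject's chair or set-up differs between visits, reach may change for reasons other than trunk control. The protocol neither rules this out nor asks for it to be recorded; the weekly diary in section 3.a(2)(l) covers medical status, medication and rehabilitation programme only.

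**Working it through.** The protocol states no figure for reach that could be reproduced. The check has three parts.

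**1. Trial-error component.** Let s be the trial-to-trial SD within a session and k the number of recorded reaches averaged per visit. Trial error contributes 2s²/k to the variance of a two-visit change.
- k = 1 (as planned): SD component √2 × s = 1.414s.
- k = 3: SD component √(2/3) × s = 0.816s.
- Ratio: 1/√3 = 0.577, a cut of 42% in SD (67% in variance). This needs no outside figure, but it assumes independent trial errors.

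For scale only, assume s = 3 cm, range 2 to 4 cm (the documents give none). The component is 4.2 cm with one reach and 2.4 cm with three. If trial error were the only source of variation, the 95% CI half-width at n = 20 would be 2.093 × SD/√20:

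| assumed s | one reach | mean of three |
|---|---|---|
| 2 cm | 1.32 cm | 0.76 cm |
| 3 cm | 1.99 cm | 1.15 cm |
| 4 cm | 2.65 cm | 1.53 cm |

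**2. Total change-score SD.** Averaging within a session leaves visit-to-visit noise (variance v per visit) and true variation in change (SD τ) untouched:

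Var(change) = 2s²/k + 2v + τ²

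Scale between-subject plus trial variance to 1, so that s² = 1 − ICC for a single reach. All values below are assumptions.
- ICC 0.70, v = 0, τ = 0.3: one reach √(0.60 + 0.09) = 0.831; three √(0.20 + 0.09) = 0.539; cut 35%.
- ICC 0.95, v = 0.10, τ = 0.3: one reach √(0.10 + 0.20 + 0.09) = 0.624; three √(0.033 + 0.20 + 0.09) = 0.569; cut 9%.
- v = 0 and τ = 0: cut 42% for any ICC.

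As an illustration, the mean change detectable at n = 20 (normal approximation, two-sided 5%, 80% power) is 2.80 × SD/√20. It falls from 0.39 to 0.36 in the second case. With ICC 0.90, v = 0 and τ = 0.3 it falls from 0.34 to 0.25.

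**3. Room in the visit.** The times come from the visit lists in section 3.b.
- Initial and 12 weeks: 5 + 5 + 60 + 10 + 10 + 5 + 5 + 5 + 5 = 110 of 120 minutes, leaving 10.
- 6 weeks, without the sailing questionnaire: 105 of 120 minutes, leaving 15.

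Two more recorded reaches per direction means 2 × 2 = 4 extra reaches per visit with one lateral side, or 2 × 3 = 6 with both sides. The protocol does not say which applies.

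**Seat.** A seat effect that is constant for a subject appears in both values and cancels in the difference. Only a change of chair or set-up between visits contributes, through v or as a shift.

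**The case against.** The strongest reply is that little depends on this. Reach is one of two measures in one of four secondary domains, in an uncontrolled pilot with no planned analysis. The test is described as routine and is done by trained staff. Random trial error lowers precision but leaves the mean change unbiased. All of that stands, and it sets the severity. It does not make the extra recordings less worth having at this cost.

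The gain can also be overread. A reader might take the 42%, or the half-widths in centimetres, as the improvement in the confidence interval for mean change. They describe one component only, on an assumed SD. Independence of trials is assumed too: drift or fatigue over five maximal reaches per direction would reduce the gain.

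A reader might further infer that differences between subjects' wheelchairs contaminate the change score and that a standard seat is needed. The documents do not support this. The design is within-subject, so stable differences between chairs cancel, and nothing indicates that chairs change over the 12 weeks. The wording about the subject's own wheelchair most naturally means the same chair each time. A standard seat would add transfers: the protocol gives no time for them, and section 6.b names a fall risk for transfers in and out of the simulator.

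Two other readings are only missing detail. Describing the forward movement and then naming lateral reach is not a contradiction. That some subjects with incomplete injuries may have no wheelchair is conjecture, and nothing prevents a chair being supplied.

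**Conclusion.** The point holds as a minor one. The protocol fixes one recorded reach per visit for a named secondary outcome, and this passes full trial-to-trial error into each subject's change. The mean of three would cut that component by 42%, given independent trials. The cut in the total change-score SD is about 9% to 35% under the assumed values (ICC 0.70 to 0.95, visit variance 0 to 0.10, true-change SD 0.3). It would be less if visit noise or true variation were larger. No SD or reliability figure in the protocol allows a firmer estimate.

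On seating, what stands is the absence of an explicit same-chair, same-set-up rule across the three assessments. The documents do not show that seating has distorted, or will distort, the measured change.

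**What to change.** In section 3.a(2)(f):
- After the practice trials, record three reaches in each direction (forward and lateral), keep the individual values and use their mean.
- Describe the lateral reach separately, including the side or sides, and say that the trial counts apply per direction.
- Test each subject in the same chair and set-up at Initial, 6 and 12 weeks, and record any change.

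Recording the two existing practice reaches would need no extra reaches. But they serve to familiarise the subject, so a mean that includes them may shift with learning between visits; fresh trials are cleaner.

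The cost is a few minutes per visit, within the 10 to 15 that the listed times leave, and some added effort or fatigue for the subject. Those times are approximate, so the margin at Initial and 12 weeks should be confirmed with the assessors. No transfer to a standard seat is required.
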